2.1.2 Phase II

- To determine the percentage of patients with chemotherapy pre-treated triple negative metastatic breast cancer treated with PLX3397 in combination with eribulin who are progression free at 12 weeks.

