For Phase II, sample size is based under the Simon's 2-stage optimal design for progression-free survival at 3 months as a single proportion. The study is designed to determine the following hypothesis with >80% power and 2-sided type I error of 5% using binomial approximation: H₀: PFS% <39% versus H_a: PFS% > 57% (with PLX3397), where PFS% is the proportion of progression-free (PFS) at 3 months. The PFS% of >57% would represent a clinically relevant improvement with the treatment in triple-negative patients with locally recurrent or metastatic breast cancer. Based on these considerations, a sample size of 51 evaluable patients is required for the study. We plan for a targeted enrollment of 56 patients with 10% dropout rate.

Interim assessment and stopping rules for Safety and efficacy

Safety and SAE data will be routinely monitored. Because of the possibility of unacceptable or excessive defined serious adverse events during treatment or the study enrollment period, stopping rules for safety/tolerability are also developed. We have set the maximum rate of treatment-related SAE at 15% in patient enrollment. Thus, we may consider terminating the study if the number of patients with SAE is greater than the number expected under the binomial distribution. The following table shows the early stopping guideline based on the number of SAE observed under the rate of unacceptable SAE in the group sequential enrolment for the study. For example, assuming the unacceptable rate of SAE is greater than 15%, if the study observes 3 or more SAE in the first 17 treated patients, then we may consider if the study should be stopped early.

Safety Stopping Rules:

Number of enrolled patients with excessive SAE to consider early study termination.

Number patients in study	1-17	18-29	30-41
Unacceptable SAE – 15%	3	4	6

Efficacy Stopping Rules

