Failure to obtain early responses at the scheduled tumor assessments will be taken as evidence that the regimen in question is ineffective. If fewer than 8 out of the first 20 pts are progression-free at 12 weeks, this would be considered an unacceptably low PFS rate (<39%), the study will not continue and accrual will cease. Accrual will continue while efficacy data is being determined. If 25 or fewer pts are progression free at 12 weeks at full accrual, then the treatment would be deemed ineffective. If the true PFS rate at 12 weeks is 39% for TNBC pts, the probability of terminating the study during the interim evaluation is 0.63; if the true PFS rate is 57% for TNBC pts, the probability that the trial will be stopped in the first stage is 0.10.

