12.2 Analysis Plan

Primary Efficacy Endpoint

Demographics and Baseline Characteristics

Demographic data (age, sex, race, ethnicity, body weight) and baseline disease characteristics will be tabulated and summarized and presented in data listings.

Progression Free Survival

Progression-free survival at 3 months (PFS) is defined as the proportion of patients alive and progression-free 90 days after Study Day 1. Duration of PFS is defined as the time from Study Day 1 to the earlier of disease progression or death due to any cause.

Progression free survival will be calculated from the first administration of PLX3397 with eribulin. The analyses of PFS will be performed using the Per Protocol population. These analyses are designed to include only objective progression events per the RECIST v1.1 criteria. Patients who do not have any post-baseline tumor assessments will be right censored on the date of Study Day 1. Patients who receive subsequent anti-cancer therapy before experiencing an event will be right censored at the date of the last tumor assessment prior to the date of initiation of subsequent therapy. Patients who have not experienced an event (and are not otherwise censored) at the time of data cutoff will be right censored on the date of their last tumor assessment

PFS will be estimated as a simple proportion based upon the results of the 12-week tumor assessment. Patients for whom this assessment is not performed will be included as failures, even if known to be alive at this timepoint. Confidence intervals will be provided. PFS and duration of PFS will also be estimated using Kaplan-Meier methods with associated confidence intervals.

Secondary and Supportive Efficacy Endpoints

Objective Response Rate

The objective response rate (ORR) is defined as the proportion of patients for whom the best overall response at the time of data cutoff is confirmed CR or confirmed PR as assessed per RECIST v 1.1 criteria. A table defining the derivation of best overall response to be applied will be provided in the SAP.

The analysis of ORR will employ the Per Protocol population. Patients who do not have any post-baseline tumor assessments will be counted as non-responders.

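### The phase II decision rule does not deliver the stated 2-sided 5% type I error, and its 39% and 57% are attached to three different time points without a source

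*Combined protocol and SAP*

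**What the plan says.** **Error and size.** Section 12.1 (Phase II) describes a Simon two-stage design for 39% versus 57% with more than 80% power and a "2-sided type I error of 5% using binomial approximation". It requires 51 evaluable patients and plans to enrol 56.

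**Decision rules.** Sections 10.1 and 12.1 stop the trial if fewer than 8 of the first 20 patients are progression-free at 12 weeks. The same bullet of section 10.1 then continues to stage 2 if at least 7 are. For a true rate of 39%, section 12.1 says that "the probability of terminating the study during the interim evaluation is 0.63"; for 57% it gives 0.10. The final rule is "If 25 or fewer pts are progression free at 12 weeks at full accrual", the treatment is deemed ineffective. No error rate is reported for these rules.

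**Time point.** The three time points are used as follows:
- 3 months: the hypothesis in section 12.1, "where PFS% is the proportion of progression-free (PFS) at 3 months".
- 90 days: the endpoint in section 12.2, "defined as the proportion of patients alive and progression-free 90 days after Study Day 1".
- 12 weeks: the primary objective in section 2.1.2 ("in combination with eribulin who are progression free at 12 weeks"), both decision rules, and the estimator in section 12.2 ("PFS will be estimated as a simple proportion based upon the results of the 12-week tumor assessment"). Section 12.1 also uses the same null here: "If the true PFS rate at 12 weeks is 39% for TNBC pts".

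No source is cited for 39% or 57%, and no conversion is given. Scans are every 6 weeks (section 8.2.3), so none is scheduled at day 90. Section 12.2 counts a missing 12-week assessment as a failure.

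**The concern.** A 2-sided 5% test conventionally leaves 2.5% for a false claim of benefit. A rule that can only declare success upward should meet that 2.5%, or the plan should say that it works at one-sided 5%. Otherwise a reader of the final report will credit a positive result with about twice the protection it has.

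The error also depends on the interim boundary, and the text supports three values for it. Finally, the null is a rate at a particular time. If 39% belongs to a later time than the one tested, the true null at 12 weeks is at least 39%, and the error is at least what the plan would compute.

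**Working it through.** **Inputs.** Null 0.39, alternative 0.57, 51 evaluable patients, first stage 20, ineffective at 25 or fewer (all section 12.1). Second stage: 51 − 20 = 31. The success bar of 26 is applied to 51 evaluable patients. Section 12.3 fits that reading: its stage sizes of 22 and 34 are close to 20/0.9 = 22.2 and 31/0.9 = 34.4.

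**Formula.** If the trial stops at r1 or fewer of 20:

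P(stop | p) = P(Bin(20, p) ≤ r1)

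P(success | p) = Σ over x from r1+1 to 20 of P(Bin(20, p) = x) × P(Bin(31, p) ≥ 26 − x)

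**The plan's own figures, and the exact error and power.**

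| Interim boundary | Stop prob. at 39% / 57% | Error at 39% | Power at 57% |
|---|---|---|---|
| Stop at ≤8 (not written; implied by 0.63/0.10) | 0.631 / 0.096 | 0.0483 | 0.801 |
| Stop at fewer than 8 (10.1, 12.1) | 0.452 / 0.040 | 0.0527 | 0.831 |
| Continue at ≥7 (10.1) | 0.280 / 0.014 | 0.0544 | 0.841 |

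Only the first row reproduces 0.63 and 0.10. It also gives power just over 80% and a one-sided error just under 5%. All three errors are about twice 0.025: 0.0483/0.025 = 1.9 and 0.0544/0.025 = 2.2.

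**Can 51 patients meet 2.5%?** With stop at ≤8, a bar of 27 gives error 0.0275, and a bar of 28 gives 0.0145 with power 0.654. A search over two-stage designs at upper-tail 0.025 and 80% power finds none at 51; the smallest needs 61. The mismatch would be visible at analysis: 26/51 counts as success, but its ordinary exact 95% lower limit is 36.6%, below 39%.

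**Time point.** The error equals one-sided 5% at a null of 39.1% (stop at ≤8), 38.8% (fewer than 8) or 38.7% (continue at ≥7). Suppose 39% holds at day T, and a share f of a constant hazard is observed after day 84:

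S(84) = 0.39 × exp(f × λ × (T − 84)), with λ = −ln(0.39)/T

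With stop at ≤8:
- Progression mostly dated at scans (f = 0.05 to 0.20, T = 90 or 91.3): null 39.1% to 39.6%, error 0.050 to 0.058.
- Smooth exponential curve (f = 1): T = 90 gives a null of 41.5% and error 0.098; T = 91.3 gives 42.1% and 0.111.

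The values of f are assumptions; the documents give none.

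**Possible origin of the rates.** Section 1.2 gives eribulin PFS medians of 2.23 months (triple-negative subgroup) and 3.7 months (overall arm, central review). Exponentially, 0.5^(3/2.23) = 0.394 and 0.5^(3/3.7) = 0.570 at 3 months. At 12 weeks the first becomes 42.4%, where the error is 0.121 (stop at ≤8).

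**Missing scans as failures.** Multiply both rates by (1 − m), with m assumed. With stop at ≤8, m = 2% gives power 0.756, and m = 8% gives error 0.017 and power 0.59.

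**Denominator.** If the bar of 26 were applied to all 56 enrolled, with 20 in stage 1, the error at 39% would be 0.120, 0.141 or 0.152 for the three boundaries in table order.

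**The case against.** **Every operative text uses 12 weeks.** The objective, the stopping rules and the estimator agree, and section 12.1 says 39% at 12 weeks. Twelve weeks can fairly be read as the working form of 3 months, six nominal days short of day 90. This stands as a reason not to lead with the time point. It does not remove the two conflicting definitions, and the phase II lead-in does not reconcile them, because section 12.2 counts from the first PLX3397 dose given with eribulin.

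**A reader might infer that the real error is 10% or more.** The documents do not support that. It needs smooth progression between days 84 and 90, whereas section 12.2 counts only objective RECIST progression events and scans are 6-weekly. Counting missing scans as failures also pulls the error down. The match of the two medians to 39.4% and 57.0% suggests a 3-month origin but does not prove it.

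**An error of 0.048 under one-sided 5% is ordinary for a discrete design.** Agreed. The fault is the 2-sided label, together with written boundaries that give 0.053 and 0.054.

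**The label might be right and the design wrong.** Honouring a 2-sided 5% would take 61 patients (minimax) or 69 (optimal). But 51 patients, 0.63 and 0.10 together reproduce a one-sided 5% design, so correcting the label is the natural reading. The sponsor should confirm it.

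**Conclusion.** The stated error is wrong for the rule as given. At a 12-week null of 39%, the upper-tail error is 0.048 to 0.054 against the 0.025 implied, whichever boundary is used. Under either written boundary it also exceeds one-sided 5%, by 0.003 to 0.004. These figures rest on 51 evaluable patients with complete 12-week assessments.

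The mixture of 3 months, 90 days and 12 weeks is a real inconsistency in the primary endpoint, and neither rate has a cited source. Its effect on the error is not established: about 0.050 to 0.058 with scan-dated progression and stop at ≤8, and 0.10 to 0.12 as the upper case under a smooth exponential curve. If 39% was meant at 12 weeks, there is no inflation from this cause.

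This should be corrected before the primary result is reported. It does not by itself call for a larger trial.

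**What to change.** 1. Reconcile the interim boundary in sections 10.1 and 12.1 with the stated 0.63 and 0.10.
2. Replace the 2-sided 5% statement with the exact one-sided error and power of the reconciled rule: 0.048 and 0.80 (stop at ≤8), 0.053 and 0.83 (stop at fewer than 8), or 0.054 and 0.84 (continue at ≥7). State that these hold for 51 evaluable patients with complete 12-week assessments, and that counting missing scans as failures lowers both error and power.
3. State that the bar of 25 or fewer applies to the 51 evaluable patients and not to all 56 enrolled.
4. Make the 12-week assessment, with a day window, the single primary time point in sections 12.1 and 12.2. Give the source and time point of 39% and 57%. If they prove to be 3-month or 90-day rates, restate both at 12 weeks and report the rule's actual error and power at those values.

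The cost is wording and one less favourable stated error. No patients or scans are added.

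### The primary proportion is reported without allowance for the two-stage design, its interval is unspecified, and the one-sided 5% cut-off is labelled two-sided

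*Combined protocol and SAP*

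**What the plan says.** Section 12.1 sizes phase II with a Simon "2-stage optimal design for progression-free survival at 3 months as a single proportion". The hypotheses are "PFS% <39% versus H_a: PFS% > 57"%, with ">80% power and 2-sided type I error of 5% using binomial approximation", and "a sample size of 51 evaluable patients is required for the study".

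The interim rule in 12.1 begins "If fewer than 8 out of the first 20 pts are progression-free at 12 weeks", in which case accrual ends. The final rule is "If 25 or fewer pts are progression free at 12 weeks at full accrual, then the treatment would be deemed ineffective". The section gives early-stopping probabilities of 0.63 at a true 39% and 0.10 at a true 57%.

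Section 12.2 then says "PFS will be estimated as a simple proportion based upon the results of the 12-week tumor assessment". Intervals are promised for the primary endpoint, but no method, level or sidedness is named, and nothing adjusts the estimate, interval or p-value for the interim stop. The only interval defined for a proportion is the 95% exact binomial one, later in 12.2, for the objective response rate.

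**The concern.** In a design that can stop early for futility, stage 1 results on the low side are frozen at 20 patients, while higher ones are diluted by further patients. The simple proportion is therefore biased, and a one-stage interval describes a sampling plan that was not used.

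The type I error is also labelled two-sided, although the decision is a single upper cut-off on a count. If the analyst takes over the 95% exact interval from the response-rate paragraph, a result that passes the rule could be printed beside an interval that includes the null. With method and level left open, that choice could be made after the count is known. This is the only primary result of a single-arm trial.

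**Working it through.** **Inputs.** From 12.1: p0 = 0.39, p1 = 0.57, n1 = 20, N = 51, so n2 = 31; ineffective if the total S is 25 or fewer, so 26 is the first passing count. Write r1 for the largest stage 1 count that stops the trial. The wording in 12.1 gives r1 = 7. Section 10.1 repeats it but also says that at least 7 is enough to continue.

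**Step 1: reproduce the plan's figures.** With X1 ~ Bin(20, p) and X2 ~ Bin(31, p):

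- P(early stop) = P(X1 ≤ r1)
- P(pass) = Σ over x > r1 of P(X1 = x) · P(X2 ≥ 26 − x)

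| | r1 = 8 | r1 = 7 (as worded) | Plan |
|---|---|---|---|
| P(early stop), 39% | 0.631 | 0.452 | 0.63 |
| P(early stop), 57% | 0.096 | 0.040 | 0.10 |
| P(pass), 39% | 0.048 | 0.053 | 5%, called two-sided |
| P(pass), 57% | 0.801 | 0.831 | >80% |

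The stated stopping probabilities match r1 = 8, not the written rule, so both are carried below. Under either, the cut-off is a one-sided test at about 5%.

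**Step 2: bias of the simple proportion.**

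E(p̂) = Σ over x ≤ r1 of P(X1 = x) · x/20 + Σ over x > r1 of P(X1 = x) · (x + 31p)/51

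For r1 = 8 and p = 0.39 this is 0.2043 + 0.1603 = 0.3645, against 0.39.

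| Bias, percentage points | r1 = 8 | r1 = 7 |
|---|---|---|
| All outcomes, true 39% | −2.55 | −2.65 |
| All outcomes, true 57% | −1.17 | −0.59 |
| Given stage 2 reached, true 39% | +4.5 | +3.1 |
| Given stage 2 reached, true 57% | +0.8 | +0.4 |

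At 26/51 the simple estimate is 51.0%. The uniformly minimum-variance unbiased estimate (UMVUE) is Σ C(19, x−1)·C(31, 26−x) / Σ C(20, x)·C(31, 26−x) over x > r1, which gives 53.6% (r1 = 8) or 52.1% (r1 = 7).

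**Step 3: lower limits set against the 39% null.** The two-stage limit solves P(pass stage 1 and S ≥ s | p) = 0.025 for the 95% interval, or 0.05 for the 90% interval.

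| Lower limit | 26/51 | 27/51 |
|---|---|---|
| 95%, ordinary exact | 36.6% | 38.5% |
| 95%, Wilson | 37.7% | 39.5% |
| 95%, Wald | 37.3% | 39.2% |
| 95%, two-stage exact, r1 = 8 | 37.0% | 38.7% |
| 95%, two-stage exact, r1 = 7 | 36.7% | 38.5% |
| 90%, ordinary exact | 38.7% | 40.6% |
| 90%, two-stage exact, r1 = 8 | 39.1% | 40.9% |
| 90%, two-stage exact, r1 = 7 | 38.8% | 40.7% |

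At 26/51 the ordinary 90% Wilson and Wald limits are 39.7% and 39.5%.

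**Step 4: separate the two causes.** The two-stage one-sided p-values at 26, 27 and 28 of 51 are 0.048, 0.0275 and 0.0145 (r1 = 8), or 0.053, 0.029 and 0.015 (r1 = 7). An upper tail of 2.5%, which a two-sided 5% test implies, is first met at 28. That is why exact 95% intervals include 39% at 26 and 27, with or without adjustment. Allowing for the interim look moves the 95% limit at 26/51 only from 36.6% to 37.0% or 36.7%. At 90% it moves the limit from 38.7% to 39.1% (r1 = 8), across the null, or to 38.8% (r1 = 7), just short of it.

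**The case against.** A reader might infer that the plan prescribes an ordinary 95% interval that contradicts its own rule. It does not: the primary interval has no stated method or level, and the 95% exact wording belongs to the response rate. The clash is what a conventional choice would produce.

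A reader might also infer that ignoring the interim look causes the clash. Step 4 shows otherwise: the adjusted 95% interval includes 39% too. At 90% an ordinary interval clashes only if it is the exact one.

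The practical reach is narrow. The decision comes from the count, only 26 and 27 of 51 are affected, and from 28/51 even the exact 95% interval excludes 39%. The bias may also be smaller than computed, because accrual continues while stage 1 is assessed. If 5 to 20 overrun patients were counted (an assumed range, r1 = 8), the bias at 39% would shrink to between −1.7 and −0.5 points.

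Finally, the UMVUE is not better in every sense. Among trials that reach stage 2, with r1 = 8, it overestimates by 11.4 points at 39% and 2.1 at 57%, against 4.5 and 0.8 for the simple proportion. These objections stand. They argue against replacing the simple proportion, not against specifying the analysis.

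**Conclusion.** The point holds as a modest defect in estimation and specification. The simple proportion is about 2.6 points low at 39% and 0.6 to 1.2 points low at 57%, over all outcomes. The 25/51 cut-off is a one-sided rule at 0.048 or 0.053, described as two-sided. As a result a conventional 95% interval at 26/51 (exact 36.6% to 65.2%), and the exact one at 27/51, would include 39% although the rule does not deem the treatment ineffective. Sidedness is the main cause. The interim look matters only at the 90% level, and full agreement at 26/51 with the two-stage limit also requires the boundary implied by 0.63 and 0.10.

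The figures assume exactly 20 patients at stage 1, 51 in total, no overrun, and ordering of final results by total count. Section 12.3 instead enrols 22 plus 34. If the cut-off of 25 were applied to 56 patients (stage 1 of 22, stopping at 8 or fewer), the one-sided alpha would be about 0.14, so the denominator needs to be settled too.

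**What to change.** In 12.1, restate the type I error as one-sided 5%. Reconcile the stage 1 boundary across 10.1, 12.1 and the stated probabilities of 0.63 and 0.10, and say that the cut-off of 25 refers to 51 evaluable patients if that is what is meant.

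In 12.2, specify an exact p-value and interval that account for the two-stage stopping rule, at two-sided 90% to match the test, with the two-sided 95% interval as a supplement. Compute them for the stage sizes actually attained. Report the UMVUE beside the simple proportion, and note that the UMVUE is the more upwardly biased of the two once stage 2 has been reached.

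The cost is a few sentences and a short program, with one more estimate to explain in the report. No further patients or data are needed.

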Informed Consent		X												
Registration			X											
History & Exam			X		X	X		X			X			X
ECOG			X		X	X		X			X			
ConMed Review			X		X	X		X	X		X	X		X
Peripheral Neuropathy		X			X			X			X			
CBC w/ 5 part diff.			X		X	X		X	X		X	X		X
Chemistry Panel	BUN, CO2, Cl, K, Na, Creatinine, Glucose (non- fasting), & Magnesium		X		X			X			X			X
Liver Function Tests	ALT, AST, AlkPhos, Total Bilirubin, & Albumin		X		X	X	X ¹⁰	X	X	X ¹⁰	X	X	X ¹⁰	X
PT/PTT ¹¹	Completed prior to tumor biopsy		X											
Pregnancy Test ²	Within 7 days of beginning treatment		X								X			
EKG ³		X						X						
Eribulin Therapy, IV ⁴	Day 1 & 8, q 21 days				X	X ⁵		X	X		X	X		
PLX3397 Therapy	Oral				Beginning With Lead-In Phase (Day -7 to -6): Daily (self-administered)									
Bone Scan & other imaging	Baseline, then as indicated	X												
CT (C/A/P)	Every 6 weeks ⁹	X									X			X
Blood for CSF1 ⁶				X	X			X			X ⁸			
Blood for Leukocyte Subtyping ⁶				X	X			X			X ⁸			
Tumor biopsy	Required for patients w/ accessible tumor		X		X (Day 0/ -1)									
Archived Tumor Tissue	Requested of all participants		X											

1. Allowed a window of ± 3 days for Day 1 procedures
2. In women of child bearing potential. Urine or Serum test allowed.
3. EKGs performed at the start of every other cycle (even numbered), at 6 week intervals
4. The following eribulin treatment delays are allowed for **patient coordination**:
C1 D8 (up to 3 days), C2+ D1 (up to 14 days), and C2+ D8 (up to 3 days)
5. A delay in C1 D8 of up to 7 days is allowed for resolution of toxicity

6. *Blood should be drawn before the first dose of PLX3397 during the lead-in phase, and before each administration of eribulin.*
7. *EOT procedures should occur within 30 days of last dose, after which the patient will be Off-Study.*
8. *Cycle 4 Day 1 only*
9. *Patients with either CR or PR and who have received at least 6 cycles of therapy may reduce the frequency of scans to every 9 weeks.*
10. *Liver function tests will be completed on D15 of the first three cycles only (C1D15, C2D15, and C3D15).*
11. *PT/PTT is only required for patients getting visceral organ biopsies*

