8.2 Assessments During Treatment

Once the patient is confirmed to be eligible based on screening assessments, the following study assessments will be performed. See Table 8-1 and 8-2 for summary. One cycle is defined as 21 days. Day 1 visit procedures for any cycle of therapy are allowed a window of ± 3 days unless otherwise noted. Following the first cycle of therapy, patients may delay the start of a new cycle of therapy up to 2 weeks as necessary for personal activities, such as travel or vacation although every attempt should be made to keep patients on schedule. Treatment or visit delays due to public holidays, weather conditions, or natural disasters, do not constitute protocol violations.

The following treatment delays are allowable for patient coordination:

- Cycle 1, Day 8 – delay eribulin administration up to 3 days
- Cycle 2+, Day 1 – delay eribulin administration up to 14 days
- Cycle 2+, Day 8 – delay eribulin administration up to 3 days

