8.2.3 During Subsequent Cycles (Cycle 2 and beyond)

The following assessments will be performed prior to receiving treatment on Day 1:

- Medical history and physical examination
- Review of concomitant medications
- Laboratories, including complete blood count, chemistry panel and liver function tests. Urine Pregnancy test will only be done for women of childbearing potential (Cycle 3+)
- Blood for CSF1 and leukocyte phenotyping (Cycle 2 and 4 Day 1 only)
- Blood for pharmacokinetics (Cycle 2, Phase Ib only)

The following assessments will be performed after receiving treatment on Day 1:

- Blood for pharmacokinetics will be drawn at 2 hours post treatment (C2, Phase Ib only)

The following assessments will take place on Day 8:

- Laboratories, including complete blood count with differential
- Review of concomitant medications

The following assessment will take place on Day 15:

- Liver function tests (Cycles 2 and 3 only)

Scans including all measurable and/or evaluable disease will be obtained every 6 weeks and at End of Treatment. Patients with either CR or PR and who have received at least 6 cycles of therapy may reduce the frequency of scans to every 9 weeks.

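### The 12-week scan that decides the Phase II primary endpoint has no window, no stated anchor when cycles are delayed, and no rule for a later progression-free scan

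*Combined protocol and SAP*

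**What the plan says.** **Endpoint (section 12.2).** "PFS will be estimated as a simple proportion based upon the results of the 12-week tumor assessment". For patients without that scan: "Patients for whom this assessment is not performed will be included as failures, even if known to be alive at this timepoint". The same section defines the endpoint as the proportion "alive and progression-free 90 days after Study Day 1" and sets the clock: "Progression free survival will be calculated from the first administration of PLX3397 with eribulin".

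**Scan timing.** Section 8.2.3: "Scans including all measurable and/or evaluable disease will be obtained every 6 weeks and at End of Treatment". Sections 5.1 and 12.1 give the same six-week interval. The CT row of Table 8-2 repeats the interval in its comment, but puts the on-treatment mark under Day 1 of the column for Cycle 3 and later.

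**Cycle timing.** Section 8.2: "One cycle is defined as 21 days". After Cycle 1, "patients may delay the start of a new cycle of therapy up to 2 weeks as necessary for personal activities". The list in 8.2 and footnote 4 of Table 8-2 allow eribulin up to 14 days late on Day 1 of any cycle from Cycle 2. The only visit window is in footnote 1: "Allowed a window of ± 3 days for Day 1 procedures".

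**Decision rules (section 12.1).** Accrual stops if fewer than 8 of the first 20 patients are progression-free at 12 weeks. The regimen is deemed ineffective if 25 or fewer are progression-free at full accrual. The stated stage 1 stopping probabilities are 0.63 at 39% and 0.10 at 57%, with 51 evaluable patients and power above 80%.

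**The concern.** One binary reading per patient feeds both the stage 1 stop and the final verdict, but its timing is not operationally defined. The six-week interval in the text and the Day 1 mark in Table 8-2 agree only while no cycle slips. Once a cycle slips, two sites following the same protocol can scan the same patient on different dates. The plan does not say which date yields the 12-week assessment, how late is too late, or what a later clean scan is worth.

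Patients who are truly progression-free at 12 weeks could then be counted as failures because of a permitted delay. With a design that has almost no power to spare, a small number of these matters.

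**Working it through.** **1. Where the scan falls.** With 21-day cycles, week 12 is nominally Cycle 5 Day 1, 84 days after Study Day 1. If scans follow cycles, each 14-day slip among Cycles 2 to 5 adds 14 days: 84, 98, 112, 126 or 140 days for zero to four slips. If scans stay on calendar weeks, the date remains day 84.

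Example: Cycle 2 starts 14 days late and nothing else moves. Cycle 3 Day 1 goes from day 42 to 56 (week 8), and Cycle 5 Day 1 from day 84 to 98 (week 14). Scanned by cycle, this patient has nothing at week 12. Scanned by calendar, the patient has a week-12 scan.

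**2. Reproducing the plan's figures.** Exact two-stage binomial, with 20 patients in stage 1, 51 in total (taking full accrual as the 51 evaluable) and success at 26 or more. With stage 1 stopping at r or fewer:

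P(stop) = P(X ≤ r), X ~ Bin(20, p)

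P(success) = Σ over x from r+1 to 20 of P(X = x) · P(Y ≥ 26 − x), Y ~ Bin(31, p)

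- r = 8: P(stop) is 0.631 at 39% and 0.096 at 57%; type I error 0.048 (one-sided); power 0.801. This matches 0.63, 0.10 and above 80%.
- r = 7, the written rule (fewer than 8): P(stop) is 0.452 and 0.040; type I error 0.053; power 0.831. The stated 0.63 and 0.10 do not reproduce.

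Both versions are carried forward.

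**3. Route A: a clean patient is scored a failure.** Let m be the share of truly progression-free patients misclassified. The documents give no rate, so m is an assumption. The observed rate is p(1 − m). At a true 57%:

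| m | Observed rate | Power, r = 8 | Stage 1 stop, r = 8 | Power, r = 7 | Stage 1 stop, r = 7 |
|---|---|---|---|---|---|
| 0 | 0.570 | 0.801 | 0.096 | 0.831 | 0.040 |
| 2% | 0.559 | 0.756 | 0.115 | 0.787 | 0.050 |
| 5% | 0.542 | 0.678 | 0.148 | 0.710 | 0.068 |
| 10% | 0.513 | 0.529 | 0.216 | 0.560 | 0.108 |

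At a true 39%, type I error with r = 8 falls from 0.048 to 0.038, 0.026 and 0.012.

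**4. Route B: the late scan is accepted as the 12-week scan.** Assume exponential PFS with 57% at day 84. The rate at day d is then 0.57^(d/84): 0.519 at day 98 and 0.473 at day 112. If every scan were that late (an upper bound), power with r = 8 would be 0.56 and 0.31. At a true 39% the rate at day 98 is 0.333 and type I error is 0.006.

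**5. 12 weeks against 90 days.** The nominal scan is at day 84. Even if the ±3-day Day 1 window applies to it, it falls on days 81 to 87, before day 90. A clean scan there does not establish status at day 90.

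**The case against.** **The scan is timed in weeks.** Every statement in the text, and the comment in Table 8-2 itself, gives weeks. Section 8.2.3 puts scans in a sentence outside its Day 1, Day 8 and Day 15 lists. ECGs, by contrast, are expressly tied to cycles in footnote 3. The CT mark cannot be literal, since a scan on Day 1 of every cycle from Cycle 3 would be three-weekly. The 14-day allowance concerns eribulin or cycle start, not imaging, and 8.2 asks that patients be kept on schedule. All of this stands. A reader might infer that the plan schedules the deciding scan on cycle days; the documents do not support that. Nor do they say that the scan stays put when the cycle moves, and the calendar invites sites to move it.

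**A slipped scan may simply be the 12-week scan.** With no window, nothing excludes this, and then the failure rule is not triggered. This stands, but it leads to route B, where the endpoint is read at a later time.

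**The plan does not mention later scans.** A reader might infer that it expressly scores failure despite a later clean scan. It does not: the clause says only that being known alive is not enough. The stronger statement follows from applying the rule literally and from silence on later scans.

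**Missing-equals-failure is conservative, and Kaplan-Meier estimates use later scans.** Both are true, so false positives are not the issue. But both decision rules count patients at 12 weeks, and the Kaplan-Meier estimate feeds neither.

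**Replacement or the analysis population would deal with such patients.** Section 12.6 replaces patients who stop without evaluation or receive too little drug. It does not reach a patient still on treatment with scans at weeks 8 and 14. The Per Protocol population named in 12.2 is not defined, so it cannot be relied on.

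**Conclusion.** The point holds as a gap in definition. The assessment that decides the primary endpoint has no window, no stated anchor when cycles are delayed, and no rule for a later progression-free scan. Whether patients are misclassified depends on how sites read the calendar, and the documents do not settle that.

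Both plausible readings push toward failure. The cost is power and a higher chance of stopping an active regimen at stage 1; the false-positive rate falls. The size rests on assumed rates. At 2% misclassification, power is already below 0.80 under either stage 1 rule (0.76 or 0.79). At 10% it is 0.53 or 0.56, and wrongful stage 1 stopping at a true 57% roughly doubles or more (0.096 to 0.216, or 0.040 to 0.108). The route B figures also assume exponential PFS and that every scan is late, so they bound the effect rather than predict it.

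**What to change.** 1. In Table 8-2 and section 8.2.3, state that scans are timed in calendar weeks from Cycle 1 Day 1 regardless of dose delays. Give the week-12 scan its own window, separate from the Day 1 visit window. Choose it together with a single time point in 12.2, so that 12 weeks (day 84) and 90 days no longer compete. A window of ±7 days around day 84, for example, would span days 77 to 91 and lie mostly before day 90, so a window alone does not settle this.
2. In section 12.2, when no scan falls in the window, let the next scan decide. Count the patient as progression-free if it shows no RECIST progression and no new anticancer therapy began before it. Count a failure if it shows progression or if there is no later evaluable scan. This cannot turn documented progression at 12 weeks into a success.
3. Report the strict missing-equals-failure result as a sensitivity analysis.

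Separately, the stage 1 wording in 12.1, the stated 0.63 and 0.10, and section 10.1 (which lets 7 progression-free patients suffice to continue) must be reconciled.

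Cost: wording, one extra analysis and no added scans. A scan may fall on a different day from a delayed Day 1 visit.
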